8.0 STUDY INTERVENTION DISCONTINUATION AND SUBJECT WITHDRAWAL/ DISCONTINUATION

8.1 Discontinuation of Study Intervention

This study may be temporarily suspended or prematurely terminated if there is enough reasonable cause. If the study is prematurely terminated or suspended, the study team will promptly inform the Study Review Board and will provide the reason(s) for the termination or suspension.

Discontinuation from study treatment does not mean discontinuation from the study, and remaining study procedures should be completed as indicated by early termination procedures in Section 8.2.3 of the study protocol. The possible reasons for early study discontinuation are listed in Section 8.2.2 and withdrawal procedure is described in Section 8.2.1. The subjects will be contacted by the study team remotely (for example, by using phone or telehealth application) to complete these procedures. If a clinically significant finding is identified (including, but not limited to changes from baseline) after enrollment, the investigator or qualified designee will determine if any change in subject management is needed. Any new clinically relevant finding will be reported as an AE. During the early termination visit upon withdrawal or discontinuation, the subject will be accessed for AEs, the use of any concomitant medications will be documented, a clinical assessment will be performed (if feasible and permitted), an assessment of COVID-19 symptoms will be conducted, a test for pregnancy in women of child-bearing potential will be completed, and any used-IP will be returned by the subject. All information will be documented in the CRF. If a study participant withdraws or is discontinued from the study, they will not be replaced.

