5.9.1 Early Termination/Hospitalization

All subjects have the right to withdraw from study participation at any time during the study. If, for whatever reason, a subject withdraws from the study or is hospitalized for increased severity of COVID-19 symptoms or other cause, an **Early Termination Visit** will be performed as deemed feasible by the PI or qualified designee.

Any AE, SAE or other medical condition or situation that occurs such that continued participation in the study would not be in the best interest of the subject will result in early termination.

The following procedures will be performed at the ***Early Termination Visit***:

1. Assess for AEs
2. Document all current medications, including medications over the counter and herbal medications
3. Perform clinical assessment (as deemed feasible if hospitalized)
4. Evaluate for increased severity of COVID-19 related disease and symptoms
5. Pregnancy Test for women of child-bearing potential

If clinical evaluation is deemed not feasible due to subject's condition, the study team will collect as much of the Early Termination Visit data and attempt to complete Day 21 and Day 28 assessments and AE assessment for those who are hospitalized and deemed off study.

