8.2.3 Procedures to be performed at the Early Termination visit

- Assess for AEs
- Document all current medications, including medications over the counter and herbal medications
- Perform clinical assessment (as deemed feasible if hospitalized)
- Evaluate for increased severity of COVID-19 related disease and symptoms
- Pregnancy test for women of child-bearing potential

If clinical evaluation is deemed not feasible due to subject condition, the Study Team will collect as much Early Termination Visit data as possible from the Electronic Medical Record

The reason for subject discontinuation or withdrawal from the study will be recorded on the CRF.

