- In-person clinical assessment will occur on study Day 1 as described in section 9.2.1 and on Day 10 as described in section 9.2.3. Remote patient visits will occur on study Day 3, 5, 7, and 9.
- Subjects to self-administer IP (Favipiravir/ Placebo) as per the instruction provided and report in diary twice daily. Site staff to assess IP adherence daily.
- Subjects to report Adverse Event and Concomitant Medications including OTC and herbal products daily.
- Site staff to assess Adverse Event and Concomitant Medications including OTC and herbal products daily
- Subject to collect oral temperature twice daily, and report in the diary.
- Subject to collect oximetry data once daily, with the caveat that if O₂ goes below 94%, an additional oximeter reading should be taken 2 hours later. If the daily O₂ saturation result is 90-93%, the subject will repeat the measurement 2 hours later. If the result is <90%, the subject is instructed to contact the study team. The study team will decide if a recheck in 2 hours is appropriate or the subject needs further medical evaluation)
- The patient's severity of COVID-19 associated symptoms will be evaluated and reported once daily, preferably at or around the same clock time, by the subject (for a period of 10 days or longer in case that the subject does not achieve the primary endpoint within the first 10 days). The study team will be reviewing the data reported by subject to ensure compliance, accuracy and completeness on days 1, 3, 5, 7, 9, 10, 14, 17, 21, 24, and 28.
- The subject will assess and score the severity of each COVID-19 associated symptom on a 4-point scale (for all symptoms besides vomiting and diarrhea: 0= none, 1= mild, 2=moderate, 3=severe. For vomiting and diarrhea: 0 = not at all, 1 = 1-2 times, 2 = 3-4 times, 3 = 5 or more times).
- Viral specimen (saliva) collection, storage and shipping (refer section 7.7 for more details).
- Refer "Schedule of Activities" table for additional information on activities and whether they are the responsibility of subjects and/or study team.

9.2.3 Treatment Day 10

In addition to procedures described in 9.2.2, the following procedures will be performed at the in-person follow-up visit on Day 10.

- Assess for AEs
- Review and assess COVID-19 signs and symptoms
- Document all current medications, including medications over the counter and herbal medications
- Document subject's status as an outpatient, subsequently hospitalized, or died

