9.2.5 Early Termination/Hospitalization

All subjects have the right to withdraw from study participation at any time during the study. If, for whatever reason, a subject withdraws from the study or is hospitalized, an Early Termination Visit will be performed.

The following procedures will be performed at the Early Termination Visit:

- Assess for adverse events
- Document all current medications, including medications over the counter and herbal medications
- Perform clinical assessment (as deemed feasible if hospitalized)
- Evaluate for increased severity of COVID-19 related disease
- Pregnancy Test for women of child-bearing potential

If clinical evaluation is deemed not feasible due to subject condition, the study team to collect Early Termination Visit data and attempt to collect Day 21 and Day 28 data and AE assessment for those subjects who are hospitalized and deemed off study.

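### Section 8.1 sends subjects who stop study drug but stay in the study to a remote early-termination list with no blood test, which conflicts with the follow-up intended elsewhere in the plan

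*Combined protocol and SAP*

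**What the plan says.** Section 8.1 makes two statements about a subject who stops taking study drug. The first is on status and route: "Discontinuation from study treatment does not mean discontinuation from the study, and remaining study procedures should be completed as indicated by early termination procedures", with section 8.2.3 given as the place to find those procedures. The second is on how they are done: "The subjects will be contacted by the study team remotely (for example, by using phone or telehealth application) to complete these procedures".

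Section 8.1 then summarises the early-termination visit. It covers adverse events, concomitant medication, a clinical assessment, COVID-19 symptoms and return of study drug, and one test: "a test for pregnancy in women of child-bearing potential will be completed". The lists in 5.9.1, 8.2.3 and 9.2.5 (Early Termination/Hospitalization) have the same content apart from drug return. Each includes a clinical assessment, as in "Perform clinical assessment (as deemed feasible if hospitalized", and each has a pregnancy test, as in "Pregnancy Test for women of child-bearing potential". None has a blood test.

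Blood is drawn on Day 1 (section 9.2.1) and Day 10 (section 9.2.3, where "the following procedures will be performed at the in-person follow-up visit on Day 10"). Footnote 2 of the Schedule of Activities allows ±1 day. The panel includes uric acid, AST, ALT and bilirubin. Clinical laboratory tests are the fourth safety endpoint in section 4.0. The safety analysis set in section 10.3 is everyone who took at least one dose.

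**The concern.** Section 8.1 is the only text that says which procedures follow once drug is stopped, and it names the early-termination list rather than the Schedule of Activities. A site that follows it to the letter makes a remote contact, completes a list without blood tests, and has no instruction to bring the subject in on Day 10.

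At stake is the laboratory safety endpoint in subjects who stop early. They belong to the safety set, and some may have stopped for tolerability, so their absence could be informative. Section 3.3 names raised uric acid as one of the two most common adverse events with favipiravir, and section 5.8 adds aminotransferase rises. Both sections describe these changes as asymptomatic, so a contact based on symptoms is poorly suited to finding them.

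**Working it through.** There is no figure in the plan to reproduce. The check sets the sections side by side.

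**1. Which procedures apply after stopping drug?** Under 8.1, the 8.2.3 list, completed remotely.

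**2. Do the early-termination lists name a blood test?**

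| Place | Pregnancy test | Blood test |
|---|---|---|
| 5.9.1 | yes | no |
| 8.1 (summary) | yes | no |
| 8.2.3 | yes | no |
| 9.2.5 Early Termination/Hospitalization | yes | no |

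The count is 0 of 4. These are in essence one list repeated, so it shows consistency, not four independent omissions.

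**3. Where is post-baseline blood drawn?** Section 9.2.3 only (Day 10 ±1). The Day 14 to 28 list in 9.2.4 and the Day 28 list in the first 9.2.5 have no draw.

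**4. Combine 1 to 3.** For a subject who stops before Day 10, the remaining procedures under 8.1 do not overlap with the scheduled draws. The literal result is no scheduled post-baseline laboratory value.

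**5. Does another route supply one?** For subjects who cannot be evaluated clinically, 8.2.3 says that "the Study Team will collect as much Early Termination Visit data as possible from the Electronic Medical Record". Those data are defined by a list with no laboratory value, so this route does not ask for one either.

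**6. Does the rest of the plan agree with the literal reading?** No.
- Section 5.9 defines completion by the last visit or procedure in the Schedule of Activities, or by hospitalisation or death.
- Section 9.2.3 does not make the Day 10 visit conditional on still taking drug.
- Section 10.5 intends follow-up to hospitalisation, death or Day 28.

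The literal reading would also drop the daily symptom entries, the saliva samples and the Day 14 to 28 visits, which cannot be squared with 10.5. So 8.1 conflicts with the plan around it.

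**7. Size.** The documents give no rate of early stopping. Assume that 2%, 5% or 10% of each arm of 625 has no Day 10 sample:
- 625 × 0.02 = 12.5, 625 × 0.05 = 31.25 and 625 × 0.10 = 62.5 subjects per arm.
- With a fraction u unsampled and an abnormality rate p among those sampled, the arm's rate lies between (1−u)p and (1−u)p + u, a width of u. The between-arm difference has width u1 + u0: 4, 10 or 20 percentage points when the fractions are equal.
- Direction: with p = 2% in both arms and u = 5% in both, the limits are 0.95 × 0.02 − 0.95 × 0.02 ± 0.05, or −5 to +5 points.

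These widths only restate the assumed fractions, as they would in any trial. They are extreme limits, not an estimate of bias.

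**The case against.** The strongest reply is that 8.1 opens by keeping the subject in the study, so the Day 10 visit still applies. Sections 5.9, 9.2.3 and 10.5 support this. So does the adherence subgroup in 10.8.3 (at most 80% of tablets taken), which presupposes outcome data from subjects who took less than the full course. This stands as evidence of intent. It does not cancel the explicit cross-reference in 8.1, which is the sentence a site would consult when a subject stops drug.

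Second, sections 9.1 and 9.2.6 send the timing of procedures and the safety evaluations to the Schedule of Activities, which has its own early-termination column. In the text available here the blood-test row of that table is damaged, so nothing is inferred from it. A mark for a blood test in that column would narrow the gap, but the table would then disagree with all four text lists.

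Third, section 5.8 says the known uric acid and aminotransferase changes reverse on stopping. A Day 10 value in someone who stopped several days earlier may miss the peak. This stands and limits the gain. A sample at the time of stopping would be more informative, but it would add a procedure and could not be taken during a remote contact.

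Fourth, abnormalities that matter clinically still reach the adverse-event record. Section 8.1 says "Any new clinically relevant finding will be reported as an AE", and 9.3.1 and 9.3.9 cover recording and follow-up. This stands for abnormalities that someone measures or that cause symptoms. It does not replace a systematic value by arm.

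A reader might go further and infer that early stoppers were in fact not sampled, or that the laboratory comparison favours favipiravir. The documents support neither. They do not show how sites read 8.1, they give no stopping rate, and the limits above are symmetric about zero.

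**Conclusion.** The point holds as an internal conflict with a modest consequence. Taken literally, 8.1 leaves subjects who stop drug before Day 10 but remain in the study without a scheduled post-baseline laboratory value, for a declared safety endpoint in members of the safety set. The surrounding sections suggest that this was not intended.

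The number of subjects affected and the direction of any bias cannot be determined from the documents. The stopping rates of 2% to 10% are assumptions that show scale only. The conclusion rests on the text lists, not on the damaged schedule row. The protocol defers analysis detail to SAP 3.1, which was not in the text reviewed, so it may already report missing Day 10 samples.

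A correction is still worth making, because it is cheap and removes an avoidable and possibly informative loss of safety data.

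**What to change.** In 8.1, replace the reference to 8.2.3 for subjects who stop drug but remain in the study. State that they continue the Schedule of Activities, including the Day 10 in-person visit and its blood draw. Reserve the 8.2.3 list, and the early-termination visit that 8.1 describes, for subjects who leave the study.

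The cost is a sentence or two. No new visit or draw is created, and section 2.1 allows the Day 10 visit to take place at the subject's home. At the assumed 2%, 5% or 10% of 1250 subjects, at most about 25, 62.5 or 125 already scheduled draws are involved.

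Section 13.0 calls version 3.0 the last version implemented during the study, so conduct may be complete. In that case the change to 8.1 cannot affect data collection. The report should then describe the laboratory safety results as excluding early stoppers who have no Day 10 sample and give their number by arm, unless SAP 3.1 already provides this. That costs one table row.

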8.2 Subject Discontinuation/Withdrawal from the Study

8.2.1 Study withdrawal procedure

All subjects are free to withdraw from participation in the study at any time, for any reason, specified or unspecified, and without prejudice. Reasonable attempts will be made by the Investigator to provide a reason for subject withdrawals. The reason for the subject's withdrawal from the study will be specified in the subject's source documents and the CRF. The study team will make every effort to contact subjects who are lost to follow-up. Attempts to contact such subjects will be documented in the subject's records (e.g., times and dates of attempted telephone contact, receipt for sending a registered letter, etc.).

8.2.2 Reasons for early study discontinuation

A subject may be discontinued from the study at any time if the subject, the study team or PI feels that it is not in the subject's best interest to continue. The following is a list of *possible* reasons for study discontinuation:

- 1) Subject decides to withdraw their consent
- 2) Occurrence of any SAE that the site investigator believes is or may be related to the study drug
- 3) Occurrence of 2 or more grade 4 or higher AE that the site investigator believes is or may be related to the study drug [CTCAE v-5 has 5 severity grades/ see attached]
- 4) Based upon the decision of the site PI: the occurrence of any medical condition or situation that is creating a situation in which continued study participation will not be in the subject's best interest
- 5) Any death of a subject that the site investigator believes is or may be related to the study drug
- 6) The subject is lost to follow-up
- 7) Subject hospitalization for any reason at any point during the 28 days of the study
- 8) The subject has become pregnant

8.2.3 Procedures to be performed at the Early Termination visit

- Assess for AEs
- Document all current medications, including medications over the counter and herbal medications
- Perform clinical assessment (as deemed feasible if hospitalized)
- Evaluate for increased severity of COVID-19 related disease and symptoms
- Pregnancy test for women of child-bearing potential

If clinical evaluation is deemed not feasible due to subject condition, the Study Team will collect as much Early Termination Visit data as possible from the Electronic Medical Record

The reason for subject discontinuation or withdrawal from the study will be recorded on the CRF.

8.3 Lost to Follow-Up

A subject will be considered lost to follow-up if he or she fails to complete more than (2) scheduled remote patient visits and is unable to be contacted by the study staff.

The following actions must be taken if a subject fails to appear for a required telemedicine study visit:

1. The Study Team will attempt to contact the subject and reschedule the missed visit and counsel the subject on the importance of maintaining the assigned visit schedule and ascertain if the subject wishes to and/or should continue in the study.

2. Before a subject is deemed lost to follow-up, the investigator or designee will make every effort to regain contact with the subject (where possible, 3 telephone calls and, if necessary, a certified letter to the subject's last known mailing address or local equivalent methods). These contact attempts will be documented in the subject's medical record or study file.
3. Should the subject continue to be unreachable, he or she will be considered to have withdrawn from the study with a primary reason of lost to follow-up.

For subjects considered lost to follow-up, the CRF will be completed up to the last contact with the subject.

9.0 STUDY ASSESSMENTS AND PROCEDURES

9.1 Efficacy Assessments

The specific timing of procedures/evaluations to be done at each study visit are found in Section of "Schedule of Activities". All assessment will be performed by the study investigators and/ or a qualified member of the study team.

9.2 Study Procedures

9.2.1 Screening, Baseline, Randomization and Treatment (Day 1)

The following procedures will be performed at the Day 1 in-person visit:

- Confirmation of positive SARS-CoV-2 test result
- Confirm subject meets all inclusion and none of the exclusion criteria
- Review the study with the subject and obtain written informed consent and Health Insurance Portability and Accountability Act of 1996 (HIPAA) authorization, or equivalent in another respective country, as applicable such as *Lei Geral de Proteção de Dados Pessoais (LGPD)* in Brazil
- Register the subject in IWRS to allot a unique subject ID (screening number)
- Randomize subject to treatment arm in IWRS as per randomization schedule
- IWRS to assign unique randomization number to the subject
- IWRS to assign IP kit number as per randomization schedule
- Record demographics (age, race, ethnicity, gender)
- Review and record medical history, surgical history
- Review and record smoking, alcohol and medication history
- Document all current medications, including medications over the counter and herbal medications
- Record height and weight
- Record COVID-19 symptoms for inclusion
- Record confirmation of positive SARS-CoV-2 test result
- Record number of days since onset of symptoms
- Collect blood sample for below listed blood tests:
 - CBC with differential, Electrolytes, BUN, Creatinine, Random Blood Serum Glucose, AST, ALT, Bilirubin, uric acid, SARS-CoV2 IgG, IL-6, IL-10, ESR, CRP, D-Dimer, ferritin. (CRP = C-reactive protein, IL-6 = Interleukin-6, IL-10 = Interleukin-10, CBC = Complete Blood Count).
 - Site do not require to wait for blood test result to randomize subjects.

- Provide the allotted IP kit, the blinded treatment (either favipiravir or placebo), and other study materials to the subject
- Assist the subject in downloading the ePRO app, create ePRO credentials for the subject, train the subject on how to use the ePRO and enter the Day 1 Dose 1 visit data with the subject during the visit to ensure the subject's understanding.
- Until the sub-study enrollment is completed (112 events have been counted), all subjects will be enrolled into the viral shedding sub-study. However, if they choose so, subjects can opt-out of participating in the viral shedding sub-study.

9.2.2 Treatment Day 1 to Day 10

- In-person clinical assessment will occur on study Day 1 as described in section 9.2.1 and on Day 10 as described in section 9.2.3. Remote patient visits will occur on study Day 3, 5, 7, and 9.
- Subjects to self-administer IP (Favipiravir/ Placebo) as per the instruction provided and report in diary twice daily. Site staff to assess IP adherence daily.
- Subjects to report Adverse Event and Concomitant Medications including OTC and herbal products daily.
- Site staff to assess Adverse Event and Concomitant Medications including OTC and herbal products daily
- Subject to collect oral temperature twice daily, and report in the diary.
- Subject to collect oximetry data once daily, with the caveat that if O₂ goes below 94%, an additional oximeter reading should be taken 2 hours later. If the daily O₂ saturation result is 90-93%, the subject will repeat the measurement 2 hours later. If the result is <90%, the subject is instructed to contact the study team. The study team will decide if a recheck in 2 hours is appropriate or the subject needs further medical evaluation)
- The patient's severity of COVID-19 associated symptoms will be evaluated and reported once daily, preferably at or around the same clock time, by the subject (for a period of 10 days or longer in case that the subject does not achieve the primary endpoint within the first 10 days). The study team will be reviewing the data reported by subject to ensure compliance, accuracy and completeness on days 1, 3, 5, 7, 9, 10, 14, 17, 21, 24, and 28.
- The subject will assess and score the severity of each COVID-19 associated symptom on a 4-point scale (for all symptoms besides vomiting and diarrhea: 0= none, 1= mild, 2=moderate, 3=severe. For vomiting and diarrhea: 0 = not at all, 1 = 1-2 times, 2 = 3-4 times, 3 = 5 or more times).
- Viral specimen (saliva) collection, storage and shipping (refer section 7.7 for more details).
- Refer "Schedule of Activities" table for additional information on activities and whether they are the responsibility of subjects and/or study team.

9.2.3 Treatment Day 10

In addition to procedures described in 9.2.2, the following procedures will be performed at the in-person follow-up visit on Day 10.

- Assess for AEs
- Review and assess COVID-19 signs and symptoms
- Document all current medications, including medications over the counter and herbal medications
- Document subject's status as an outpatient, subsequently hospitalized, or died

- Perform clinical assessment and review reported vital signs (oral temperature, heart rate and oxygen saturation)
- Collect blood sample for below listed blood tests:
 - CBC with differential, Electrolytes, BUN, Creatinine, Random Blood Serum Glucose, AST, ALT, Bilirubin, uric acid, SARS-CoV2 IgG, IL-6, IL-10, ESR, CRP, D-Dimer, ferritin. (CRP = C-reactive protein, IL-6 = Interleukin-6, IL-10 = Interleukin-10, CBC = Complete Blood Count).

